3.9 Safety

For the DB period, summary tables by DB treatment group will be provided on the Safety population.

For the Active Treatment Cycle, summary tables by number of active treatment cycles will be provided on the Active Treatment population. Additionally, a summary table will be also provided by dose received at each active treatment cycle on the Active Treatment population.

The summary tables will follow the strategy specified in Section 3.1.

3.9.1 *Extent of exposure*

To describe the duration of exposure, three durations of exposure will be calculated.

- Duration of study treatment exposure will be defined in weeks as:
(The date of last visit attended – treatment cycle 1 injection date + 1) / 7.
- Duration of treatment cycle will be defined in days as:
For subjects who are retreated at the end of the cycle, the duration of treatment cycle is calculated as (date of retreatment) - (treatment injection date).
For subjects who are not retreated at the end of the cycle, the duration of treatment cycle is calculated as (last attended visit date of the treatment cycle) – (treatment injection date) + 1.
- Duration of Active Treatment exposure will be defined in weeks as:
(The date of last visit attended – first Dysport injection date + 1) / 7.

The following summary tables will be provided:

- Description of study treatment exposure by DB treatment group + overall subjects on the safety population for DB period and overall subjects for the whole active treatment periods.
Study treatment exposure will be described both as a quantitative and qualitative variable.

- Description of duration of treatment cycle, for each treatment cycle, dose received of each treatment cycle and overall subjects from the safety population.
- Description of duration of treatment cycle, by dose received at the cycle and all doses combined on the active treatment population.
Active Treatment exposure will be described both as a quantitative and qualitative variable for each period of exposure.
- A summary table with the total number of subjects who received 1, 2 or 3 active treatment cycles and the total number of subjects who received at least 1, 2 or 3 active treatment cycles, all doses combined on Active treatment population and by DB treatment group + overall subjects.

To describe the doses received, the following summary tables will be provided:

- Description of the actual dose received in each cycle by DB treatment group and overall subjects from the safety population.
The number and percentage of subjects receiving the actual dose will be provided.
- Description of the actual dose at each active treatment cycle, by treatment received for the active treatment cycle and overall subjects from the safety population.
The number and percentage of subjects receiving the actual dose will be provided for each active cycle.
- A listing of exposure data will also be provided.

3.9.2 *Adverse events*

Adverse events will be coded using the Medical Dictionary for Regulatory Activities (MedDRA) latest version (23.0 or later) and presented by MedDRA preferred term and system organ class.

AEs will be classified as treatment-emergent AEs (TEAEs) according to the rules below:

- Events with start date (and time) on or after the date (and time) of first IMP administration.
- Events whose severity worsens on or after the date (and time) of first IMP administration.

A TEAE that occurs under a particular treatment cycle and worsens in intensity under a different treatment cycle will be considered as treatment emergent under the two treatment cycles. In the event of another occurrence of a TEAE with a change in intensity under a different treatment cycle, the subject will also be counted in that different treatment cycle. A given AE will be assigned to the dose received prior to the onset of the AE in the designated treatment cycle.

An overall summary table of all adverse events will be presented (as described in Section 3.9) and include the following:

- Subjects with any TEAEs,
- Subjects with any TEAEs by maximum intensity,
- Subjects with any TEAEs related to IMP,
- Subjects with any TEAEs related to IMP by maximum intensity,
- Subjects with any TEAEs leading to drug withdrawal,
- Subjects with any SAEs,

- Subjects with any TEAEs leading to death,
- Subjects with any SAEs related to IMP,
- Subjects with any TEAEs of special interest (AESIs).

This summary table will be also be provided by dose received at each active treatment cycle.

All TEAEs will be summarized with the number and percentage of subjects with adverse events classified by primary system organ class and preferred term. The number of occurrences of a TEAE will also be presented. This summary table will also be provided by dose received at each active treatment cycle.

Summary tables will also be presented by SOC and PT for SAEs, TEAEs by intensity, TEAEs by causality, and non-serious TEAEs with at least 2 subjects. TEAEs will also be summarized by decreasing overall PT frequency

If the intensity or causality is missing for a TEAE, it will be considered as missing in the summary tables. In the event of multiple TEAE being reported by the same subject within the same SOC/PT, the maximum intensity (severe > moderate > mild > missing) and the most serious causality (related > not related > missing) will be chosen.

Listings will be presented and sorted by DB treatment group, subject ID, start date of AE, primary system organ class, preferred term and verbatim text for all adverse events recorded during the study. Other information collected, such as end date and outcome of AE, will be provided in the listings.

Listings of SAE, adverse events leading to discontinuation from the study, clinically significant events, adverse events leading to drug withdrawal and death will also be presented.

TEAEs will be identified in the adverse events listings. Pre-treatment AEs and clinically significant AEs will also be flagged in the AE listings.

Adverse Events of Special Interest (AESIs)

Adverse events of special interest (AESIs) for Dysport in this study are defined as:

- Any TEAE that suggests a possible remote spread of effect of the toxin, or
- Any TEAE related to urinary incontinence or faecal incontinence, or
- Any TEAE assessed as a potential hypersensitivity reaction,

where there is a reasonable possibility of causal relationship with treatment with Dysport, regardless of the investigator reported causality.

The method described below is used for identification and analysis of events that may be qualified as TEAEs that suggest a possible remote spread of effect of the toxin, events related to incontinence or faecal incontinence or events suggestive of hypersensitivity like reactions.

TEAEs due to possible remote spread of the effects of Dysport will be identified using the list of MedDRA preferred terms (PTs) compatible with the mechanism of action of BTX-A and based on the recommendations from the Committee for Medicinal Products for Human Use (CHMP) and the Food and Drug Administration (FDA). TEAEs potentially representing hypersensitivity reactions will be identified using the Standardised MedDRA Query (SMQ) (narrow search query) for hypersensitivity reactions. TEAEs that are possibly related to urinary incontinence or faecal incontinence will also be identified using the list of MedDRA preferred terms.

The list of MedDRA preferred terms used to identify any potential AESI is provided in *AESIs MeDDra.xlsx*.

All TEAEs identified using the search strategy described above will be medically evaluated during the study before the database lock and unblinding, by the sponsor to identify events which could possibly represent “remote spread of effect of toxin”, or which are suggestive of “related to urinary incontinence or faecal incontinence” or “hypersensitivity reactions” due to study treatment administration. Events will be disregarded as an AESI if they are confounded by the presence of alternative clinical aetiologies (medical history, concomitant medication or diagnosis which could account for the symptoms); if they are considered to be local effects instead of distant spread, as judged by the site of injection; the time period between the last study treatment administration and event onset is not in accordance with the expected mechanism of action; or due to insufficient information/evidence to make an assessment.

In the summary data tabulations and listings, only the final list of AESIs confirmed by the sponsor as “a possible remote spread event”, “hypersensitivity reactions” or “urinary incontinence and faecal incontinence” will be taken into account.

Besides the AESI listing, a summary table of AESI will be presented by SOC and PT (as described in Section 3.9) and include the following:

- Subjects with any AESI suggesting a possible remote spread of effect of the toxin,
- Subjects with any AESI related to urinary incontinence or faecal incontinence,
- Subjects with any AESI assessed as a potential hypersensitivity reaction.

3.9.3 ***Laboratory data***

All laboratory data will be presented in the units of International System of Units (SI).

The following summaries will be provided:

- A summary of the actual and change from baseline in each laboratory parameter by treatment group and timepoint,
- A summary of the number and percentage of subjects experiencing Potentially Clinically Significant Abnormalities (PCSA). PCSA criteria for laboratory parameters are defined in appendix 2,

For PCSA table, the denominator should be the number of subjects with both a baseline and a post-baseline assessment at a given timepoint.

In addition, the following listings will be provided:

- A listing of all laboratory data. Out-of-reference-range values will be flagged as high (H), low (L), clinically significant [C]. Any unscheduled laboratory assessments will be flagged as such in the listings.
- Laboratory reference ranges,
- A listing will present all values of the parameter for a subject with at least a clinically significant abnormal value for hematology and biochemistry.
- A listing of PCSA. All data for a laboratory parameter will be displayed for a subject having at least one post-baseline PCSA (with flag indicating PCSA).
- A listing will present the urine drug screening and urine pregnancy test.
- A listing will be provided for subjects with abnormal result of drug abuse test.

Any clinically significant laboratory result abnormalities observed during the study will be reported as AEs.

3.9.4 *Vital signs*

Vital signs were recorded at the Screening Visit. A listing of vital sign data by treatment group, with unscheduled vital signs flagged.

Any clinically significant vital sign abnormalities observed during the study will be reported as AEs.

3.9.5 *Physical examination*

Physical examination was done at the Screening Visit. Date of exam and overall assessment will be listed and sorted by DB treatment group, and subject ID, with unscheduled physical examination flagged.

Any clinically significant physical examination finding observed during the study will be reported as AEs.

3.9.6 *Antibodies*

The following definitions will be considered:

- **Seroconverters** are subjects with ADA titer ≤ 1 for antibody at baseline and ADA titer > 1 post-treatment.
- **Seroreverters** are subjects which ADA titer > 1 at baseline and ADA titer ≤ 1 post-treatment.
- **Treatment boosted ADA** are subjects with ADA titer > 1 at baseline that were boosted to a higher-level following IMP administration (the ADA titer is greater than 100 times the baseline titer).
- **Incidence** is defined as the proportion of seroconverters or treatment-boosted subjects.

The following conventions will be considered:

- Percentage of seroconverters and incidence should be calculated using the number of subjects with a baseline and at least one ADA assessment post-treatment.
- Percentages of seroreverters and Treatment boosted ADA should be calculated using the number of subjects with ADA titer > 1 at baseline and at least one ADA assessment post-treatment.

The following summaries of ADA data will be provided:

- An overall summary of ADA status for binding and neutralizing with:
 - number and percentage of baseline results with titer > 1 ,
 - quartiles of the titer range,
 - number of seroreverters,
 - number of treatment-boosted,
 - number and percentage of seroconverters,
 - incidence.

A shift table from baseline to EOS/EW visit with the number and percentage of subjects separately for binding and neutralising ADA will be provided.

The following listings should be provided:

- A listing of any ADA data, including baseline BTX status (if the subject has previously received any treatment with BTX), and the status and titer for binding ADA and titer for neutralizing ADA,
- An overall ADA status of each subject,
- A listing for all subjects with binding ADA results with titer > 1 post baseline. This listing will include the combined information about baseline BTX status, primary efficacy results and TEAEs,
- A listing for all subjects with neutralizing ADA results with titer > 1 post baseline. This listing will include the combined information about baseline BTX status, primary efficacy results and TEAEs,

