### *3.1.1.1 Definitions of Clinically Significant Adverse Event and Dose Limiting Event*

A clinically significant AE is defined as:

- Drug-related severe AE or drug related serious AE
- Treatment emergent faecal incontinence, defined as new onset faecal incontinence that lasts for more than 4 days and that in the investigator's opinion is not due to any other cause e.g. diarrhoea

- Treatment emergent urinary incontinence, defined as: new onset, or a significant and sudden deterioration in any pre-existing urinary incontinence in the investigator's opinion, that lasts for more than 4 days and that in the investigator's opinion is not due to any other cause.

A DLE for the purpose of this study is defined as a clinically significant AE that would preclude another drug administration at the same dose level in a given subject.

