### 3.1.1.2 *DRC Meetings*

A DRC will be established to make recommendations for dose escalation, dose de-escalation, progression from Stage 1 to Stage 2 or study termination in Stage 1 of the clinical study (see Section 13.3.1 for the composition and operation of the DRC). The maximum dose to which escalation will be permitted will be 800 U.

If no subject reports a clinically significant AE in a cohort, the DRC will meet once all PVD2 and PVD1 evaluable subjects of a dose level have reached Week 6 to review the unblinded efficacy and safety data and recommend the dose for the next cohort. The DRC may recommend to reassess the previously used dose level based on the review of efficacy and safety data from the cohort(s).

If any subject reports a clinically significant AE (as defined in Section 3.1.1.1), then further enrolment into the cohort, as well as retreatment in open label cycles at current dose, will be suspended and an ad hoc DRC meeting will be scheduled.

During the ad-hoc meeting, the DRC will review blinded data of the subject(s) with clinically significant AE and all available efficacy and safety data from the cohort. The DRC may request to break the blind to confirm if the significant AE is a DLE, and based on this assessment, if enrolment in the cohort may continue.

At the end of Cycle 1-Week 6 visit for all subjects in Stage 1, the DRC will meet to review all safety and efficacy data from the cohort(s) and recommend the two doses to be assessed in Stage 2. The DRC will also recommend if further PVD1 cohort(s) are required or if PVD1 subjects should be removed from Stage 2.

In Stage 2 of the study, ad hoc DRC meetings will be scheduled to review efficacy and safety data in the event of an emergency safety issue.

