### 3.2 Primary and Secondary Endpoints and Evaluations

#### 3.2.1 Primary Endpoints and Evaluations

##### Stage 1

- Safety endpoints between Baseline and Cycle 1-Week 6, including the incidence of any DLE.

##### Stage 2

- Mean change from Baseline to Cycle 1-Week 6 in the vaginal dilator induced pain as reported on an 11-point numeric rating scale (NRS) (using the dilator maximum tested size (DMTS) reported at Baseline).

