### 3.2.3 Safety Endpoints and Evaluations

The safety and tolerability of Dysport will be assessed throughout the study by evaluating:

- Incidence of treatment emergent AEs (TEAEs), serious AEs (SAEs), clinically significant AEs, DLEs, AEs (or SAEs) leading to discontinuations and AEs of special interest (AESIs).
- Absolute values, values classified as abnormal/normal and change from Baseline in the clinical laboratory test results (including nonfasting clinical biochemistry and haematology parameters).
- Number of subjects who seroconvert for BTX antibodies following treatment with Dysport.
- Clinical evaluation of concomitant medication usage (except rescue medication) and therapies.

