### 7.1 Primary Endpoint(s) and Evaluation(s)

For Stage 1, the primary endpoint is safety between baseline and Cycle 1-Week 6.

For Stage 2, the primary efficacy endpoint is the mean change from Baseline to Cycle 1-Week 6 in the vaginal dilator induced pain as reported on an 11-point numeric rating scale (NRS) (using the dilator maximum tested size (DMTS) reported at Baseline).

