#### 11.4.7 Safety Evaluation

All safety data will be included in the subject data listings. Analyses and summary tables will be based upon the safety population.

All AEs will be coded according to the current version of MedDRA at the time of database lock and will be classified by MedDRA preferred term and system organ class. AE listings will be presented by subject, system organ class and preferred term.

Incidence of all reported TEAEs and SAEs will be tabulated by treatment, group, dose and overall. In addition, summary tables will be presented by maximum intensity, drug relationship and TEAEs associated with premature withdrawal of study medication.

A TEAE is defined as any AE that occurs during the active phase of the study if:

- it was not present prior to receiving the first dose of IMP, or
- it was present prior to receiving the first dose of IMP but the intensity increased during the active phase of the study.

All TEAEs will be flagged in the AEs listings.

Summary statistics (mean, median, SD and range as appropriate) by treatment group, dose and by overall will be presented for clinical laboratory tests at each assessment with change from Baseline. For laboratory data, abnormal values will be flagged in the data listings and a list of clinically significant abnormal values will be presented. Shift tables will be presented of the number and percentage of subjects with low, normal or high values and normal or abnormal exams.

The number and percentage of subjects with the presence of BTX-A antibodies (neutralising) at Baseline will be presented. The number of seroconverters (subjects who have negative results at Baseline and have at least one positive result at any one post-treatment timepoint) for neutralising antibodies will be reported.

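### The SAP plans no output that reports the Stage 1 primary endpoint: no table of DLEs or clinically significant AEs, no DLE flag, and no safety table cut at Cycle 1-Week 6

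*SAP*

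**What the plan says.** Protocol 3.2.1 defines the Stage 1 primary endpoint as "Safety endpoints between Baseline and Cycle 1-Week 6, including the incidence of any DLE". Section 7.1 repeats the Week 6 window. Section 3.2.3 separately names the incidence of clinically significant AEs and of DLEs among the safety endpoints. A DLE is "a clinically significant AE that would preclude another drug administration at the same dose level in a given subject" (3.1.1.1), so it is a subset of clinically significant AEs.

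Protocol 11.4.7, which sets out the safety analysis, is narrower: "Incidence of all reported TEAEs and SAEs will be tabulated by treatment, group, dose and overall". It adds tables by intensity, relationship and withdrawal, but mentions neither DLEs nor Week 6.

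SAP 3.9 sets the reporting window: "For the DB period, summary tables by DB treatment group will be provided on the Safety population". Further tables go by active treatment cycle or by dose received in each cycle. SAP 3.9.2 continues: "An overall summary table of all adverse events will be presented (as described in Section 3.9) and include the following". Nine rows follow: any TEAE, the same by maximum intensity, related TEAEs, the same by maximum intensity, TEAEs leading to withdrawal of drug, SAEs, deaths, related SAEs and AESIs. The SOC/PT and AESI tables add no row for DLEs or clinically significant AEs. Clinically significant AEs get a listing and a flag in the AE listing.

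**The concern.** The study closed after cohorts 1 to 6. The DRC's view, quoted in SAP 1.3.5, was that efficacy could not be assessed from cohorts of this size. Safety is therefore the main result the study can deliver, and DLE incidence by dose to Week 6 is the part the protocol names. If the SAP is followed to the letter, that figure appears in no output.

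Two things would be lost. DLE status would stay unknown at any dose with at least one clinically significant AE. TEAE percentages on the primary window would also be missing, because the planned tables use a longer window that differs between subjects. SAP section 5, which records departures from the protocol, says nothing about either.

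**Working it through.** **1. Endpoint against outputs.**

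| Protocol requires | SAP provides |
|---|---|
| DLE incidence to Cycle 1-Week 6 (3.2.1) | No table, listing or flag. DLE appears only in the abbreviations and in the sample-size text of 1.3.2 |
| Incidence of clinically significant AEs (3.2.3) | Listing and flag only (3.9.2) |
| Safety between Baseline and Week 6 (3.2.1, 7.1) | Whole double-blind period, or active treatment cycles (3.9) |

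SAP 3.8.1 sets aside a primary efficacy analysis because the Stage 1 objective is safety, but no section then states a primary safety analysis. For efficacy, SAP 3.8 does name Weeks 6 and 12 as the main timepoints.

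**2. Window.** Retreatment is possible from Week 12 at the earliest. A subject never retreated stays in Cycle 1 until Week 36 (protocol Table 2, footnote a). Ratios to the endpoint window: 12/6 = 2 and 36/6 = 6. Early withdrawals can be shorter.

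**3. What can be recovered.** Because DLEs are a subset of clinically significant AEs, a dose with none listed has 0 DLEs, and AE start dates show which events fell before Week 6. Related TEAEs by intensity, related SAEs and incontinence AESIs approximate much of the clinically significant AE definition. They are not equivalent: the sponsor screens AESIs and can discard them for insufficient information, and the AESI rows do not apply the protocol's more-than-4-days rule. Withdrawal of drug is not the DLE criterion, which concerns another administration at the same dose level.

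**4. The plan's own DLE figures (SAP 1.3.2).** Confidence that the true rate is at most p after 0 DLEs in n is 1 − (1 − p)^n. The exact one-sided 80% upper bound is 1 − 0.2^(1/n).

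- n = 8, p = 0.18: 1 − 0.82^8 = 79.6%; bound 18.2%. The 18% reproduces to rounding.
- n = 16, p = 0.09: 1 − 0.91^16 = 77.9%; bound 9.6%. The SAP claims at least 80%.
- With a uniform prior the exponent is n + 1: 1 − 0.91^17 = 79.9% at n = 16, and 1 − 0.82^9 = 83.2% at n = 8.

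**5. The same bounds at the planned numbers, for illustration.** Active subjects, cohorts 1 to 6: 100 U, 8; 300 U, 8; 400 U, 8 + 6 = 14; 500 U, 8 + 8 = 16; total 46. Pooled placebo: 6 × 2 = 12.

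| Dose | n | 80% upper bound, 0 DLEs | 80% upper bound, 1 DLE |
|---|---|---|---|
| 100 U | 8 | 18.2% | 33.0% |
| 300 U | 8 | 18.2% | 33.0% |
| 400 U | 14 | 10.9% | 19.9% |
| 500 U | 16 | 9.6% | 17.6% |

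The 1-DLE column is the exact (Clopper-Pearson) bound, the 0.8 quantile of Beta(2, n − 1). One DLE nearly doubles the bound at each dose, so the design statements cannot be applied to the results unless DLEs are counted by dose. At 400 U, 9% with 14 subjects would carry 1 − 0.91^14 = 73.3%; the SAP sentence itself refers to 16.

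**The case against.** The best reply has five parts.

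- **The SAP follows protocol 11.4.7**, which plans no DLE table and no Week 6 cut, so there is arguably no change to declare. Protocol section 11 also lets a major modification be reported in a dedicated CSR section. It is true that the gap starts in the protocol, between 3.2.1 and 11.4.7. The SAP is still where the endpoint has to become an output.
- **DLEs served dose escalation, which is over**, and the DRC noted no safety concerns. That lowers the stakes. It does not remove the primary endpoint from an analysis of Stage 1 that is still going ahead.
- **A reader can count from the listings, and the double-blind tables contain every event up to Week 6.** Both are true for clinically significant AEs. Neither settles DLE status where such an event occurred, nor gives a percentage on the endpoint window. Follow-up after closure ends 12 weeks after the last dose, so some Cycle 1 windows end near Week 12, which is the lower end of the 2-to-6-fold range.
- **The 9% is nearly right under a uniform prior (79.9%).** That is still short of at least 80%, and the point is secondary.
- **Assigning DLE status now is retrospective, and the AESI review sees only events retrieved by its search terms.** This stands and shapes the fix.

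Table shells, the eCRF and the DRC charter were not available, so it cannot be excluded that DLE status is collected.

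**Conclusion.** The point holds on all three counts: no table of DLEs or clinically significant AEs, no DLE flag, and no safety table cut at Cycle 1-Week 6. It should be fixed before database lock. It is a missing output and not evidence of a hidden safety signal. Its reach is limited to DLE status at any dose with a clinically significant AE, and to TEAE percentages on the primary window. Early termination accounts for dropping Stage 2, the intermediate and primary analyses and the per-protocol set, but not this endpoint. The conclusion rests on the SAP text alone. The illustrative bounds assume planned active numbers, which replacements or an extra accepted subject could change.

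**What to change.** In SAP 3.9.2:

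- Add a Safety-population table of n/N (%) of subjects with at least one DLE and with at least one clinically significant AE, with onset from first injection to the Cycle 1-Week 6 visit. If that visit is missing, use Day 48, the end of its window (Day 43 + 5). Columns: 100, 300, 400 and 500 U, all Dysport, pooled placebo.
- Repeat the TEAE overview with the same cut. Keep the full double-blind tables, which protocol 3.2.3 also needs.
- Flag DLEs in the AE listing and state the source: the DRC determination where one exists, otherwise a written rule applying the protocol 3.1.1.1 definition unchanged. The sponsor's medical review before lock and unblinding, already planned for AESIs, is a suitable place, provided it is extended to every flagged clinically significant AE.
- Record the addition in section 5 as reconciling protocol 3.2.1 with 11.4.7.

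Exact one-sided 80% upper bounds are optional. If shown, use the actual number treated per dose and correct the 9% statement.

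The cost is SAP wording, two tables and a flag. The main work is assigning DLE status, since the protocol says only that "The DRC may request to break the blind to confirm if the significant AE is a DLE", so a determination may not exist for every event.
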